#### 1.2 PURPOSE OF THE STUDY

A number of therapeutic interventions targeting inflammatory signalling might reduce the severity of the inflammatory response phase resulting in amelioration of the lung damage thereby averting respiratory failure

IRAS: 282552 Page **18** of **57** 

and the need for mechanical ventilation. This trial aims to evaluate the efficacy of two inhibitors of key signalling pathways using drugs which are already licensed for use in other clinical indications.

#### 1.3 RATIONALE FOR THE STUDY POPULATION

Patients with COVID-19 infection in the community may be asymptomatic or experience only mild transient symptoms which do not merit experimental therapeutic intervention. Patients who are admitted to hospital due to the severity of their symptoms are invariably in the inflammatory phase of the disease with dyspnoea and/or hypoxia indicating involvement of the lower respiratory tract. Data from our own hospital as well as Chinese and Italian experiences indicate that around 30% of hospitalised patients will deteriorate during their admission resulting in the need for ventilatory support. The study population is therefore selected to evaluate whether the experimental treatments are effective in prevention of clinical deterioration in a hospitalised population.

#### 1.4 RATIONALE FOR THE LONG COVID SUB-STUDY

With the global impact of the COVID-19 pandemic our understanding of the SARS-COV2 pathogen is continually evolving. COVID-19 is well recognized as a respiratory and multi-organ disease, caused by marked systemic inflammation. Despite the advances in the acute management of COVID-19, our understanding of the post-acute COVID-19 syndrome (PACS) is poorly understood.

Post-acute COVID-19 syndrome is defined as persistent symptoms of COVID-19 which have developed during or after infection, that continue for more than 12 weeks and are not explained by an alternative diagnosis. COVID-19 is well recognised as a multi-organ disease (Gupta *et al.*, 2020), with severe disease being characterised with marked and progressive systemic inflammation (Qin *et al.*, 2020). Similarly, the range of symptoms of PACS represents the multi-organ impact of the syndrome and include; fatigue, myalgia, autonomic dysfunction, gastrointestinal manifestations, anxiety/depression and altered concentration (Nalbandian *et al.*, 2021).

The underlying pathophysiology of PACS is not known, but suggested mechanisms include chronic dysregulation of the immune system subsequent to the acute infection. Studies have identified immunological dysfunction in patients with 'long covid' at 8 months from acute infection with highly activated innate immune cells. This is reflected by 4 cytokines which were most associated with symptomatic long covid-19 patients; IL-6, interferon gamma, MCP-19 and VCAM-1.

Immune exhaustion has also been suggested as a mechanism for 'long covid'. Immune exhaustion has been observed in other chronic infections as a result persistent inflammatory signal exposure, including chronic hepatitis and HIV (Ramakrishnan *et al.*, 2021). This leads to impairment in functionality of CD4 and CD8 T-cells.

Immune exhaustion has also been seen in patients with COVID-19 with increased levels of PD-1 and Tim-3 being shown in patients with severe COVID-19 (Diao *et al.*, 2020), (Ueland *et al.*, 2021). Similar results have been seen at 8 months in patients with 'long covid' with raised levels of sTIM3 and PD-1, as well as raised level of T-cell activation proteins, IFN 1 and 3, as well as their downsteam chemokines CXCL9 and CXCL10 (Phetsouphanh *et al.*, 2021).

We will therefore explore the impact of RUX or FOS on the long term outcome from COVID-19 infection including overall survival and other co-morbidities such as VTE, diabetes, hypertension and long-COVID.

#### 2 STUDY OBJECTIVES

#### 2.1 PRIMARY OBJECTIVE

The primary objective is to determine the efficacy of RUX and FOS to reduce the proportion of hospitalised patients progressing from mild/moderate to severe COVID-19 pneumonia. A modified WHO COVID-19 Severity Ordinal Scale (COVID-19 Therapeutic Trial Synopsis published 18th February 2020) will be used to grade clinical deterioration from Hospitalised Mild Disease (<5) to Hospitalised Severe Disease (≥ 5). The modification includes an additional grade for Hospitalised Severe Disease that allows the capture of clinical deterioration in patients for whom escalation in organ support is not offered. Patients are eligible for recruitment to MATIS at grades 3 or 4. These patients stand to gain the greatest benefit from inflammatory signal inhibitors that may ameliorate the cytokine storm and prevent organ failure.

Table 1. Modified WHO COVID-19 Severity Scale, from the WHO R&D Blueprint

Patient state Descriptor		Grade
Uninfected	No clinical or virological evidence of infection	0
Ambulatory	No limitation of activities	1

MATIS version 4.0 dated 2nd November 2022

IRAS: 282552 Page **20** of **57** 

	Limitation of activities	2
Haspitalisad mild disease	Hospitalised, no oxygen therapy	3
Hospitalised mild disease	Oxygen by mask or nasal prongs	4
	$SpO_2$ < 90% on $FiO_2$ $\geq$ 60% by face mask	5
Hospitalised severe disease	Non-invasive ventilation, CPAP or high-flow oxygen	6
	Intubation and mechanical ventilation	7
	Ventilation + additional organ support (vasopressors, RRT, ECMO)	8
Dead	Death	9

Published in the COVID Therapeutic Trial Synopsis, February 18th 2020

#### 2.2 SECONDARY OBJECTIVES

- Determine the efficacy of RUX or FOS to reduce mortality
- Determine the efficacy of RUX or FOS to reduce the need for invasive ventilation and/or ECMO
- Determine the efficacy of RUX or FOS to reduce the need for non-invasive ventilation including CPAP or high flow nasal oxygen
- Determine the efficacy of RUX or FOS to reduce the proportion of patients suffering clinically significant oxygen desaturation
- Determine the efficacy of RUX or FOS to reduce the need for renal replacement therapy
- Determine the efficacy of RUX and FOS to reduce the incidence of venous thromboembolism COVID-19 pneumonia
- Determine the efficacy of RUX and FOS to improve the severity of COVID19 pneumonia on a modified
   WHO COVID19 Ordinal Scale
- Determine the efficacy of RUX or FOS to reduce the level of inflammatory biomarkers
- Determine the efficacy of RUX or FOS to reduce blood ferritin, CRP, LDH and D-dimer
- Determine the efficacy of RUX or FOS to reduce the level of serum creatinine.
- Determine the efficacy of RUX or FOS to reduce duration of hospital admission
- Evaluate the safety of RUX and FOS for COVID19 pneumonia

IRAS: 282552 Page **21** of **57** 

[figure not shown]

- Determine the impact of RUX or FOS to reduce the development of the post-acute COVID-19 syndrome
  in patients who presented with mild-moderate COVID-19 pneumonia
- Determine the impact of RUX or FOS on long term (12-18 months) survival
- Determine the ability of RUX or FOS to reduce the development of the post-acute COVID-19 syndrome
  in patients who presented with mild-moderate COVID-19 pneumonia
- Assess impact of signal inhibitors (RUX or FOS) on health related quality of life at 6 and 12, 18 months post COVID-19

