2.7 Descriptive statistics for outcome measures

The proportion of participants with the primary outcome of WHO COVID- $19 \ge 5$ by day 14 will be summarised by treatment arm and repeated for day 28. This will be undertaken for stage I and stage II.

In addition, the proportion of participants experiencing each of the components of the WHO COVID-19 severity scale score (mortality, invasive ventilation plus organ support (renal replacement therapy, ECMO or inotropic support), invasive ventilation, non-invasive ventilation including CPAP and high flow nasal oxygen) at any point up to day 14 (repeated up to day 28) will be summarised by treatment arm. This will be undertaken for stage I and stage II.

Trajectories of mean (SD) grades over time by treatment arm will also be plotted. This will be undertaken for stage II only.

Time spent at each of the components will be summarised as medians and IQRs by treatment arm. This will be undertaken for stage II only.

All stage 1 analysis of the WHO COVID-19 grades will be completed by the independent statistician in Newcastle University to ensure the trial statistician remains blind and only DMC members will see these results.

Inflammatory markers CRP, LDH, ferritin, D-dimer, and serum creatinine values will be summarised by treatment arm over time and presented as means (SD) and median (IQR). This will be undertaken for stage II

Summaries (means (SD) and median (IQR)) of length of stay will be tabulated amongst those that do not withdraw or die. This will be undertaken for stage II

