3.1 Primary outcome of the main study - Modified WHO grading

3.1.1 Definition of the primary outcome

The proportion of participants progressing from mild to severe COVID-19 pneumonia within 14 days. Where severe COVID-19 pneumonia is defined by a modified WHO COVID-19 Ordinal Score ≥ 5 (on the 9 point scale), comprising the following indicators of disease severity: Death (9) OR Requirement for invasive ventilation plus organ support (8) Requirement for invasive ventilation (7) OR Requirement for non-invasive ventilation including CPAP or high flow oxygen (6) OR O₂ saturation < 90% on \geq 60% inspired oxygen (5). These are captured in the database as follows:

Modified WHO COVID-19 Ordinal Score	Database
(9) Death	
(8) Requirement for invasive ventilation plus organ support	Has the patient required renal replacement therapy? OR Has the patient required ECMO? OR Has the patient required inotropic support? AND Has the patient required intubation and mechanical ventilation?
(7) Requirement for invasive ventilation	Has the patient required intubation and mechanical ventilation?
(6) Requirement for non-invasive ventilation including CPAP or high flow oxygen	Has the patient required NIV, CPAP or high flow nasal oxygen?
(5) O ₂ saturation < 90% on ≥60% inspired oxygen	Has the patient's oxygen saturation been < 90% on 60% inspired oxygen?

3.1.2 Statistical model at stage 1

The stage one primary analysis will consist of fitting two separate binomial regression models for the RUX vs SOC and FOS vs SOC comparisons in order that we can undertake an adjusted analysis using a propensity score approach. Specifically a generalized linear model with WHO COVID-19 status (<5 or ≥ 5) as the outcome and treatment group as a covariate. We will adjust the treatment effect for the

following prespecified covariates using a propensity score approach. The propensity score model will include:

- baseline WHO COVID-19 score (3 or 4)
- age ($<65 \text{ or } \ge 65$)
- receipt of dexamethasone (prior randomisation or up to 1 day post randomisation)
- receipt of tociluzimab (prior randomisation or up to 1 day post randomisation)

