3.2.5 Continuous laboratory values

For inflammatory markers of CRP, LDH, ferritin, D-dimer and serum creatinine levels a linear mixed effect model will be used to estimate the mean difference in values between intervention arms (RUX and FOS) and SOC at each follow-up visit (day 1, day 7 and day 14). Participants will be included as a random intercept with fixed effects for time, time-by-treatment arm interaction and baseline values. Stratification variables age and site, plus receipt of known effective treatments dexamethasone and/or tociluzimab, prior vaccination against COVID-19, and receipt of paxlovid and/or molnupiravir at the time of or prior to randomisation into MATIS will also be included as fixed effects. Baseline adjusted treatment group differences with 95% confidence intervals will be presented for each time-point.

For example for CRP the model to be fitted to estimate the treatment effect at each visit up to day 14 will be:

$$\begin{split} Y_{ijt} = \ \beta_0 + \ \beta_1 R U X_{ij} + \ \beta_2 F O S_{ij} + \ \beta_3 C R P_{ij}^0 + \ \beta_4 A G E_{ij}^0 + \ \beta_5 D E X_{ij}^0 \\ + \ \beta_6 T O C_{ij}^0 + \ \beta_7 V A C_{ij}^0 + \ \beta_8 P A X_{ij}^0 + \ \beta_9 M O L_{ij}^0 \ \beta_{10} time_7 \\ + \ \beta_{11} time_{14} + \ \beta_{12} R U X_{ij} * time_7 + \ \beta_{13} R U X_{ij} * time_{14} \\ + \ \beta_{14} F O S_{ij} * time_7 + \ \beta_{15} F O S_{ij} * time_{14} + \ \beta_{16} S I T E_1 \\ + \ \beta_{17} S I T E_2 + \dots + \ \beta_{18} S I T E_{j-1} + b_{1,i} + e_{it} \end{split}$$

for

t = 1 to 3 time points (day 1, 7 and 14), i = 1 to 30 participants

 RUX_{ij} : dummy variable for treatment ($RUX_{ij} = 0 \text{ or } 1$) for participant i

 FOX_{ij} : dummy variable for treatment ($FOS_{ij} = 0 \text{ or } 1$) for participant i

 CRP_{ij}^{0} : baseline CRP value for participant i

 DEX_{ij}^0 : dummy variable for receipt of dexamethasone at the time of or prior to randomisation (includes day of randomisation or one day post randomisation) ($DEX_{ij} = 0 \text{ or } 1$) for participant i TOC_{ij}^0 : dummy variable for receipt of tociluzimab at the time of or prior to randomisation (includes day of randomisation or one day post randomisation) ($TOC_{ij} = 0 \text{ or } 1$) for participant i VAC_{ij}^0 : dummy variable for prior vaccination against COVID-19 at the time of or prior to randomisation (includes day of randomisation or one day post randomisation) ($VAC_{ij} = 0 \text{ or } 1$) for participant i

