 PAX_{ij}^0 : dummy variable for receipt of paxlovid at the time of or prior to randomisation (includes day of randomisation or one day post randomisation) ($PAX_{ij} = 0$ or 1) for participant i

 MOL_{ij}^0 : dummy variable for receipt of molnupiravir at the time of or prior to randomisation (includes day of randomisation or one day post randomisation) ($MOL_{ij} = 0$ or 1) for participant i $time_x$: dummy variable for time (= 0 or 1) at time point x days. Day 1 is represented by $time_7 = 0$ and $time_{14} = 0$

Site_i: dummy variable for each of the jth sites

$$b_{1,i} \sim N(0, \sigma_{b1}^2), e_{it} \sim N(0, \sigma_e^2)$$

Where $b_{1,i}$ is the random intercept at the participant level. Each of $b_{1,i}$ and e_{it} are assumed to follow normal distributions. An unstructured covariance matrix will be used and the model will be fitted using restricted maximum likelihood (REML). This model makes assumptions about random effects distributions, correlation structures and residuals, which will all be investigated. If the model fails to converge model estimates will not be presented.

The above will be repeated for each inflammatory marker up to day 14 and additionally up to day 28.

References

- 2. Siddiqui O. Statistical methods to analyze adverse events data of randomized clinical trials. *Journal of Biopharmaceutical Statistics* 2009; 19: 889-899. DOI: http://dx.doi.org/10.1080/10543400903105463.
- 4. White IR, Royston P and Wood AM. Multiple imputation using chained equations: Issues and guidance for practice. *Statistics in Medicine* 2011; 30: 377-399. DOI: https://doi.org/10.1002/sim.4067.
- 5. Kahan BC. Accounting for centre-effects in multicentre trials with a binary outcome when, why, and how? *BMC Medical Research Methodology* 2014; 14: 20. DOI: 10.1186/1471-2288-14-20.
- 6. Kahan BC and Morris TP. Improper analysis of trials randomised using stratified blocks or minimisation. *Stat Med* 2012; 31: 328-340. 2011/12/06. DOI: 10.1002/sim.4431.

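### Serum creatinine is analysed with no rule for values taken after renal replacement therapy starts, so a difference in renal failure between arms is diluted and, under particular conditions, reversed

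*Protocol*

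**What the plan says.** Protocol 2.2 lists two renal objectives side by side: "Determine the efficacy of RUX or FOS to reduce the need for renal replacement therapy" and "Determine the efficacy of RUX or FOS to reduce the level of serum creatinine". Creatinine is also a listed outcome at days 14 and 28 (Protocol 3.3; SAP 1.1.3 and 3.2).

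SAP 3.2.5 gives the model: "For inflammatory markers of CRP, LDH, ferritin, D-dimer and serum creatinine levels a linear mixed effect model will be used to estimate the mean difference". On its terms it says: "Participants will be included as a random intercept with fixed effects for time, time-by-treatment arm interaction and baseline values". Age, site, dexamethasone and/or tocilizumab, vaccination and the two antivirals are further fixed effects. The day 28 extension reads "The above will be repeated for each inflammatory marker up to day 14 and additionally up to day 28"; creatinine is not named there, but SAP 3.2 lists it at day 28.

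The descriptive plan in SAP 2.7 is "Inflammatory markers CRP, LDH, ferritin, D-dimer, and serum creatinine values will be summarised by treatment arm over time", also without reference to RRT. The blood-measurement model in SAP 2.8 has no RRT term either.

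RRT itself is recorded. The database item in SAP 3.1.1 is "Has the patient required renal replacement therapy", and SAP 3.2.3 analyses RRT as a yes/no outcome at days 14 and 28. Protocol 7.7 covers patients with GFR below 15 ml/min, on or off dialysis, so new RRT during follow-up is foreseeable.

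**The concern.** Starting RRT means that the kidneys have failed, yet it lowers the creatinine reading. Followed as written, SAP 3.2.5 takes that lower reading as an ordinary observation. The same event therefore counts as a bad outcome in SAP 3.2.3 and as a fall in creatinine in SAP 3.2.5. The missing-at-random property of the mixed model does not help, because the value is observed.

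At stake is how one secondary efficacy result is read. A drug that prevents renal failure would receive too little credit in the creatinine comparison, and in some circumstances a lower mean creatinine could be taken as renal benefit when it is not. The concern is RRT begun after randomisation. Patients already on dialysis at entry raise a related question, addressed in the fix.

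**Working it through.** **1. The plan's own figure.** There is none to reproduce: the documents give no effect size, standard deviation or RRT rate for creatinine. Every creatinine value and rate below is an assumption. The only document input is 152 patients per arm (Protocol 3.1).

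**2. Is there a rule elsewhere?** Post-randomisation events have a stated analysis in Protocol 4.2 and SAP 3.1.5, but only for co-enrolment and COVID-19 treatments, and only for the primary outcome. SAP 2.7, 2.8 and 3.2.5 contain no exclusion, censoring or covariate for RRT.

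**3. Dilution.** Assume 80 µmol/L in other patients, new RRT in 10% versus 5%, and RRT for every patient with renal failure. The difference in arm means is (0.10 − 0.05) × (value − 80).

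| Before RRT | On RRT | Without the dialysis effect | Observed | Lost |
|---|---|---|---|---|
| 500 | 250 | 0.05 × 420 = 21.0 | 0.05 × 170 = 8.5 | 1 − 8.5/21.0 = 60% |
| 400 | 250 | 0.05 × 320 = 16.0 | 8.5 | 47% |
| 500 | 350 | 21.0 | 0.05 × 270 = 13.5 | 36% |
| 400 | 350 | 16.0 | 13.5 | 16% |

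The sign is kept in every row.

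**4. Test statistic.** Lower dialysed values also reduce the variance. With s the assumed SD within each group, p the RRT share and g the gap from 80, the arm variance is s² + p(1 − p)g². For 500 falling to 250 and s = 25:
- Without the dialysis effect: (625 + 0.09 × 420² + 625 + 0.0475 × 420²)/152 = 25,505/152 = 167.8, so z = 21.0/12.95 = 1.62.
- Observed: (625 + 0.09 × 170² + 625 + 0.0475 × 170²)/152 = 5,223.75/152 = 34.4, so z = 8.5/5.86 = 1.45.

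The fall in z is 1 − 1.45/1.62, about 10%. With s = 40, z goes from 1.56 to 1.24. With s = 25, it goes from 1.59 to 1.45 for 400 to 250, and from 1.62 to 1.57 for 500 to 350.

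**5. When the sign reverses.** Let f be the share with renal failure, d the share on RRT, c0 = 80 the value in other patients, cA the undialysed value in renal failure and cD the dialysed value. The arm mean is (1 − f)c0 + (f − d)cA + d·cD. The difference, arm with more RRT minus the other, is Δf(cA − c0) − Δd(cA − cD); a positive value counts against the arm with more RRT.
- Failure 12% versus 8%, all dialysed: 0.04 × (cD − 80), which is +6.8 at cD 250 and −0.8 at cD 60. It vanishes as cD nears 80 and reverses only below 80.
- Failure 10% in both arms, RRT 8% versus 4%: −0.04 × (cA − cD), from −2.0 (400 to 350) to −17.6 (500 to 60), where the true difference is 0.
- Failure 12% versus 8%, RRT 10% versus 2%: 0.04 × (cA − 80) − 0.08 × (cA − cD). This is 12.8 − 12.0 = +0.8 for 400 to 250, 16.8 − 20.0 = −3.2 for 500 to 250, and 16.8 − 12.0 = +4.8 for 500 to 350.
- Patients with a baseline of 400 who start dialysis, 4 percentage points more of them in one arm: 0.04 × (cD − 400), which is −10 at cD 150 and −2 at cD 350.

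**6. Simulation.** A reduced form of the SAP model was fitted (baseline, visit, arm by visit, random intercept; 152 per arm; cA 500, cD 250; 150 runs). Mean day 14 differences, in µmol/L:
- Failure 12% versus 8%, none dialysed: +16.1.
- The same, all dialysed: +6.7.
- The same, 85% versus 25% of failures dialysed: −1.9 (negative in 56% of runs).
- Failure 10% in both arms, 80% versus 20% of failures dialysed: −16.4.

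**The case against.** The strongest reply is that nothing is hidden. RRT and mortality are separate secondary outcomes, modelled at days 14 and 28 in SAP 3.2.3, so an excess of dialysis would appear beside the creatinine result. The objective, read literally, is the level of creatinine, and SAP 3.2.5 attaches no significance threshold to it, only estimates with 95% intervals. All this stands and limits the harm. It does not correct the creatinine estimate, and nothing in the SAP tells the reader to interpret the two together.

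A reader might infer that the arm with more renal failure will look better. The documents do not support that: they give no RRT rates, and where RRT follows renal failure equally in both arms the arithmetic shows dilution with the sign kept. The trial is open label (Protocol 3), so unequal use of RRT cannot be excluded, but that makes reversal possible rather than expected.

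A reader might also infer that deaths pull the arm mean down as dialysis does. Death produces missing values, not low ones, and in this model a patient's earlier high values still inform the estimate. The lack of a rule for death is a separate and weaker concern.

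Finally, replacing the mixed model by a ranking of death, RRT and creatinine would go too far. Its top ranks repeat outcomes already analysed. Visits after discharge are not mandated (Protocol Table 7, SAP Table 1), so recovered patients may have no value to rank. Patients on dialysis at entry would also need their own rule.

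**Conclusion.** The gap is real and confined to one secondary laboratory endpoint. SAP 3.2.5 has no rule for creatinine after post-randomisation RRT, and by default dialysed values enter as ordinary observations. The expected consequence is dilution: 36% to 60% of the mean difference in the three main scenarios, 16% for a shallow fall from 400 to 350, and a smaller loss in the test statistic (about 10% for 500 to 250 with an SD of 25). Reversal is conditional. It needs unequal use of RRT among patients with similar renal failure, or dialysed values near normal or below the patient's own baseline. When all renal failures are dialysed in both arms, the sign changes only if the dialysed value falls below that of other patients. All sizes rest on assumed values. The primary outcome, the sample size and the error rates are untouched.

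**What to change.** In SAP 3.2.5:
- State that creatinine values after the first post-randomisation RRT are not taken as measured kidney function. Keep the mixed model and describe its estimate as a difference in measured level.
- Add a pre-specified ordinal or rank-based analysis at days 14 and 28, with the same covariates, in which death and newly started RRT rank as worse than any measured creatinine.
- For that analysis, state how discharged patients without a blood test are handled, and analyse patients on dialysis at baseline separately or exclude them.
- Report the number on new RRT by arm and visit beside the creatinine result, and do not interpret a lower mean creatinine as benefit unless the two agree.

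The cost is SAP wording and one extra model. RRT and death are already collected. The item "Has the patient required renal replacement therapy" does not show on its face whether RRT is new or chronic, and Protocol 9.1 asks for days of use for ventilation but not for dialysis. The team should confirm that the case report form separates new from chronic RRT and dates its start, or at least places it by visit. No treatment, visit or sample size changes.
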